Since this study constitutes a clinical trial, although we are not studying experimental drugs, the intervention is experimental with the risks described in the Human Subjects section. Therefore, it is appropriate to have a Data and Safety Monitoring Board (DSMB) to monitor the study with an attendant monitoring plan as outlined below. The role of the DSMB will be to ensure that no unexpected untoward consequences of the intervention occur, and if they do, to implement safeguards to decrease or eliminate future risks. Any adverse events will be provided to the DSMB in real time. These adverse events include, but are not limited to, self-injurious behavior or inappropriate or threatening behavior with parents, or clinicians or research staff. Less serious adverse events related to the intervention will be compiled and summarized for the DSMB at their scheduled meetings. All other severe adverse events will be monitored by the principal investigator, the study coordinator, and the assessment team and will be reported to the DSMB regardless of a priori expectation or investigator assessment of likelihood of the study being the cause of the adverse event. The DSMB also will have the power to request further data from the principal investigator based on any concerns raised in the ongoing investigation. At any time during the study, based on its findings, the DSMB can put the study on either temporary hold or stop the study entirely after notifying the principal investigator and the IRB. In the rare case in which they must do so, the DSMB will generate a formal report to the principal investigator, the sponsor, and the IRB. This report would then be modified for a lay reader, a version for past participants and current participants would be produced, and the letter would be sent to all past and current study participants. The DSMB will first meet at the beginning of the study to review its charge and activities. It will then meet quarterly to review non-serious and serious adverse event rates, as well as preliminary efficacy data. It also will meet on an ad hoc basis if the real-time serious adverse events warrant meeting, in their judgment. The format of the meeting will include a presentation of the summarized data by the Principal Investigator ([name]) and the

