biostatistician ([name]). The absolute rates of adverse events as well as the rate compared between the intervention and control groups will be presented. The Board will be composed of two faculty at Penn who are not associated with this intervention but have familiarity with autism intervention, and a senior staff member from Philadelphia's early intervention program.

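### A safety board with power to stop the trial sees efficacy data every quarter, co-presented by the principal investigator, with no closed session, boundary or non-binding statement

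*Combined protocol and SAP*

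**What the plan says.** All of the board's procedures are in the Data and Safety Monitoring Plan, at the end of the protocol.

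- **Role.** It is framed as safety: "The role of the DSMB will be to ensure that no unexpected untoward consequences of the intervention occur". No efficacy role is described.
- **Content of the meetings.** After a first meeting on its charge, the board's schedule is: "It will then meet quarterly to review non-serious and serious adverse event rates, as well as preliminary efficacy data".
- **Power.** At any time, "based on its findings, the DSMB can put the study on either temporary hold or stop the study entirely", once the principal investigator and the IRB have been notified.
- **Presenters.** "The format of the meeting will include a presentation of the summarized data by the Principal Investigator"; the sentence goes on to name the biostatistician as co-presenter.
- **By-arm display.** For adverse events it is explicit: "The absolute rates of adverse events as well as the rate compared between the intervention and control groups will be presented". For efficacy, nothing is said either way.
- **Members.** Two Penn faculty with no link to the intervention but familiar with autism treatment, "and a senior staff member from Philadelphia's early intervention program". No member is described as a statistician.

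The plan contains no efficacy or futility boundary, no alpha adjustment, no closed session and no statement that efficacy looks are descriptive only. Statistical Analysis for Aim 1 and Statistical Power do not mention interim looks; the latter assumes alpha 0.05, two-tailed.

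**The concern.** Two separate things are at stake.

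**Decisions.** A body that sees efficacy results, and may stop the trial on its findings, can make an efficacy decision that nobody planned. Without a rule, the final test at 0.05 would not have its nominal error rate if an earlier look had been acted on.

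**Delivery.** The principal investigator is in the room. Under Clinician training, Penn consultants hold bi-weekly group consultations and make monthly field visits with feedback to clinicians in the ImPACT arms. Parent outcomes, including parents' use of the coached strategies, are measured at 3 months, so mid-trial data on the target of that coaching will exist. The study team cannot avoid knowing which agency is in which arm. It can avoid knowing which arm is ahead.

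The protocol describes the study as a pilot that should support an application for a larger trial. It states no need for an early efficacy decision, so the looks bring some risk for little gain.

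**Working it through.** **1. The plan's own figure.** The plan gives no interim error rate, boundary or number of looks, so there is nothing of that kind to reproduce. The only related figure is the two-sided alpha of 0.05 in Statistical Power.

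**2. Error rate if looks were treated as tests.** Let K be the number of looks, the final analysis included. Under the null hypothesis, with equal information between looks, the statistic at look k is

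Z_k = (e_1 + … + e_k) / √k, where the e_j are independent standard normal.

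Type I error is the probability that |Z_k| > 1.96 for at least one k from 1 to K. From 1,000,000 simulated sequences, for one outcome and one contrast:

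| K | Every look at 0.05 | Interim looks at \|z\| > 3.29, final at 1.96 |
|---|---|---|
| 1 | 0.050 | 0.050 |
| 2 | 0.083 | 0.050 |
| 3 | 0.107 | 0.050 |
| 4 | 0.126 | 0.051 |
| 6 | 0.154 | 0.051 |
| 8 | 0.177 | 0.052 |

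The row K = 1 recovers the nominal 0.05. The right-hand column (a Haybittle-Peto rule) shows that looking does not in itself inflate the error. The exposure comes from looking without a rule.

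**3. What K could be.** Study length, accrual and number of meetings are not stated. Child measures are scheduled at baseline and 6 months, and parent measures at baseline, 3 and 6 months. If all 54 families enrolled together (an assumption), parent outcomes would have two informative looks (0.083) and child outcomes only one (0.05). Staggered enrolment would give more looks, but not equally spaced in information. The values for 4 to 8 looks are therefore the upper part of a conditional range.

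**4. How informative a look would be.** The plan has 18 children per arm. The half-width of a 95% interval for a standardized difference is 1.96 × √(2/n), with n per arm and no baseline adjustment.

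- n = 18: 1.96 × √(2/18) = 0.65
- n = 9 (half with outcomes, an assumption): 1.96 × √(2/9) = 0.92

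With the plan's intra-class correlation of 0.05 and 3 children per clinician, the design effect is 1 + (3 − 1) × 0.05 = 1.10. Multiplying by √1.10 = 1.049 gives 0.69 and 0.97. Clustering by agency would widen these further; adjustment for baseline would narrow them by an amount that the plan does not allow one to compute. Statistical Power expects child effects of 0.34 to 0.70. At half information, the half-width exceeds that whole range.

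**5. The passages side by side.** The role is safety; the content includes efficacy; the power to stop follows from findings in general. By-arm comparison is specified for adverse events and left open for efficacy. The plan shows a route from the study team to delivery (the consultants), but does not say that interim results travel along it.

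**The case against.** The strongest reply is that this is a safety board described in safety terms. The stopping power sits among sentences on adverse events, its use is called rare, and it triggers a formal report and a letter to participants. No efficacy test is planned at any look. A reader might infer that the board is set up to stop for benefit; the documents do not support that. What remains is that the literal wording does not confine the power to safety, and efficacy data are on the agenda.

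Other inferences that go further than the text:

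- *The principal investigator presents alone.* No: the biostatistician co-presents. The principal investigator is nonetheless present and sees what is shown.
- *The principal investigator sees efficacy by arm.* Not stated. Nothing prevents it, and the board may ask the principal investigator for more data.
- *The principal investigator's team trains the consultants.* The plan gives that task to a person whose name is removed and the MSU research team. It shows only that Penn consultants coach the clinicians.
- *Coaching will change.* Not stated. Consultation frequency is fixed, MSU staff check the consultants' fidelity twice a month, and the coders of the PICCOLO and the parent adherence checklist are blind to arm and time point. These limit the risk; none of them keeps interim results from the people who direct the coaching.

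It is also fair to say that imprecise looks are unlikely to persuade a board to act. That lowers the chance of an efficacy decision, but it equally removes the reason for showing the data.

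**Conclusion.** The point holds as a defect in the monitoring procedure. Followed as written, the plan brings efficacy data each quarter to a board with a safety role and an unrestricted power to stop, with the principal investigator present and no rule for what those data may lead to.

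Its size is conditional. The range 0.083 (2 looks) to 0.126 (4) to 0.177 (8) assumes equally informative looks, each tested at two-sided 0.05, for one outcome and one contrast; the number of looks is my assumption. A reader might conclude that the trial's type I error will be 0.13 to 0.18. The documents do not support that: no such tests are planned, and the measurement schedule may give few informative looks. If no look is acted on or treated as a test, alpha stays at 0.05.

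The effect on delivery cannot be put in numbers. It needs efficacy to be shown by arm and the knowledge to influence coaching, and the plan states neither. It is a plausible risk that wording can reduce, and this should be done before efficacy data go to the board.

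**What to change.** In the Data and Safety Monitoring Plan and the board's charter, do one of the following:

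- **Preferred.** Remove efficacy data from the quarterly review, and limit it to adverse events, recruitment, retention and data quality.
- **If efficacy is kept.** Have the biostatistician alone present it, in a closed session without the principal investigator. State that it is descriptive and that the trial will not stop for benefit or futility.

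Leave the board's safety powers unchanged in either case.

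The cost is wording only: sample, visits and analysis are untouched. The downside is that the principal investigator does not see any interim efficacy results shown to the board. The change does not by itself stop the research team, which receives the surveys and videos, from looking at incoming outcomes.

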In Philadelphia, children ≤36 months of age with ASD are eligible for treatment through the infant and toddler early intervention program. Risk is determined using the Modified Checklist for Autism in Toddlers. Thirteen agencies provide these services. They use an interdisciplinary treatment approach, have a treatment philosophy that supports parent-mediated intervention, and provide home-based services. The early intervention system projects that >800 children with autism ≤36 months of age will receive services next year. On average, children receive 3.4 hours/week of services, about one hour of which comprises "specialized instruction," which Project ImPACT will replace. Children will retain all other services. In specialized instruction, therapists: 1) design learning environments and activities that promote skill acquisition; 2) plan activities that address the outcomes on the individualized family service plan; 3) provide families with information, skills and support to enhance child skill development; and 4) work with the child and family to enhance the child's development. Specialized instructors typically are bachelors-prepared individuals with early child development training.

Aim 1: Compare outcomes in young children (social communication and development) and their parents (stress and self-efficacy) randomized to one of three groups: A) treatment as usual, B) Project ImPACT delivered at 1 hour/week and C) Project ImPACT delivered at 4 hours/week.

Overview

We will compare the outcomes of young children and their parents randomized to three groups: A) treatment as usual, B) 6 months of Project ImPACT at 1 hour/week and C) 6 months of Project ImPACT at 4 hours/week. Observations of regular early intervention sessions between families and clinicians will provide evidence of adherence to the Project ImPACT intervention. Observations of parent and child interactions as well as direct assessments with enrolled children over the course of 6 months, will give information on changes in social communication and parent responsiveness and self-efficacy.

Sample

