Following introductory training, clinicians in each agency will participate in bi-weekly group consultation meetings with Penn consultants (see below) via videoconferencing. During these 1-hour group meetings, clinicians will present their Project ImPACT cases to the other clinicians in their agency and receive feedback and problem solving from the Penn consultant. Each clinician also will receive a monthly consultation visit in the field. During these 1-hour sessions, the consultant will observe an intervention session, complete the coaching fidelity form, and provide feedback to the clinician on Project ImPACT implementation. [name] team has successfully used this remote consultation model to train clinicians to fidelity in Project ImPACT with high ratings of satisfaction, self-efficacy, and attendance from clinicians who participated in the training.⁴¹

To prepare Penn staff to consult in the field, [name] and the MSU research team will train them to fidelity in Project ImPACT and its coaching model, and fidelity monitoring. This training will include the same introductory training described above, consultation meetings with MSU study staff to provide feedback on program implementation with a family with ASD via videoconferencing; and obtaining reliability on parent treatment adherence and coaching fidelity scoring for master session tapes. Once Penn staff have been trained to fidelity in coaching and reliability in fidelity monitoring, they will meet biweekly with MSU staff via video-conferencing for supervision as they provide monthly consultation sessions to community clinicians using Project ImPACT. MSU research staff also will conduct twice-a-month cross-site video-based fidelity checks to ensure that Penn staff is providing training and feedback to the clinicians implementing the program in a way that is consistent with the Project ImPACT model.

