All unexpected adverse events will be reported by study personnel to the DPH IRB, the Project Officer at IES, and the IRB at Penn via standard adverse event reporting procedures. All adverse reactions will be noted and discussed thoroughly with the PI, mentors, and IRB to determine proper reporting procedures on a case-by-case basis.

Potential Benefits of the Proposed Research to the Participants and Others

There are some benefits to family/child and clinician participants. Families in the treatment conditions will receive training in intervention techniques considered best practice for young children with ASD. In addition, clinicians in the two treatment conditions will receive considerable training and support throughout their participation that has the potential to benefit the children they treat. The potential exists for great benefits to child-serving systems at large. Potential risks are reasonable given the safeguards proposed and the valuable information to be yielded regarding interventions for children with ASD.

Data and Safety Monitoring Plan

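### Adverse event rates are compared between groups with no common enquiry and no denominator, although reporting channels and session time differ by arm

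*Combined protocol and SAP*

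**What the plan says.** The Data and Safety Monitoring Plan has the board meet quarterly and says of the data shown to it: "The absolute rates of adverse events as well as the rate compared between the intervention and control groups will be presented". It does not say whether a rate is per child, per month or per hour of contact. The examples of events are "self-injurious behavior or inappropriate or threatening behavior with parents, or clinicians or research staff", introduced as a list that is not exhaustive.

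On who finds and passes on events, the Adverse Events section says "All unexpected adverse events will be reported by study personnel". The Data and Safety Monitoring Plan adds "All other severe adverse events will be monitored by the principal investigator, the study coordinator, and the assessment team", and for milder events "Less serious adverse events related to the intervention will be compiled and summarized for the DSMB at their scheduled meetings".

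The section on data to be collected from human subjects lists field observations, questionnaires, video-based assessments and a service-use interview with parents (at screening, 3 months and 6 months). None of these is described as asking about adverse events.

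The arms differ in contact. Aim 1 sets usual treatment against "B) Project ImPACT delivered at 1 hour/week and C) Project ImPACT delivered at 4 hours/week". Under Clinician training, trained clinicians attend bi-weekly group meetings at which they present ImPACT cases to study consultants, and "Each clinician also will receive a monthly consultation visit in the field".

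**The concern.** A rate comparison between randomized groups is fair only if an event has the same chance of being recorded in each group. Here, recording depends on events reaching study personnel by whatever route exists, and the routes are not the same. Both ImPACT arms have a regular case meeting with study consultants that usual care is not described as having. The 4-hour arm also has more session time in which a clinician could notice an event.

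The board may put the study on hold or stop it. With 18 children per arm, a few extra recorded events would change the picture it sees. An excess produced by better detection could be taken for harm. Conversely, a real excess could be dismissed as detection, because crude rates cannot separate the two.

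**Working it through.** The plan states no adverse event rate, threshold or contact ratio, so there is no figure of that kind to reproduce. The related count does reproduce: 2 agencies × 3 clinicians × 3 children = 18 children per arm.

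**Inputs from the protocol**
- Study sessions: 1 or 4 h/week for 6 months (Cluster Randomized Study Design), taken as 26 weeks.
- Usual services: 3.4 h/week on average, about 1 h of it specialized instruction. ImPACT replaces that hour and all other services continue (Setting for all Research Activities).
- Case meetings: bi-weekly, read as every two weeks, for ImPACT clinicians only (Clinician training).

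**Contact by arm.** All services = 3.4 − 1 + study-session hours.

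| Arm | Study sessions, h/week | Over 26 weeks | All services, h/week | Over 26 weeks |
|---|---|---|---|---|
| Usual care | 1 | 26 | 3.4 | 88.4 |
| ImPACT 1 h | 1 | 26 | 3.4 | 88.4 |
| ImPACT 4 h | 4 | 104 | 6.4 | 166.4 |

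- 4-hour v usual care: 104/26 = 4.0 for study sessions; 166.4/88.4 = 1.88 for all services.
- Both ImPACT arms pooled v usual care: [(1 + 4)/2]/1 = 2.5 for study sessions; [(3.4 + 6.4)/2]/3.4 = 1.44 for all services.
- Case meetings: 26/2 = 13 for ImPACT clinicians, none described for usual care.

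**Effect on the apparent rate.** Let f be the share of reference-arm events detected only in clinician contact, and R the contact ratio. With no true per-hour difference, the apparent rate ratio is (1 − f) + f × R. The documents do not give f, so the whole range is shown for the 4-hour arm v usual care.

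| f | R = 4.0 | R = 1.88 |
|---|---|---|
| 0 | 1.00 | 1.00 |
| 0.25 | 1.75 | 1.22 |
| 0.5 | 2.50 | 1.44 |
| 0.75 | 3.25 | 1.66 |
| 1 | 4.00 | 1.88 |

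For the pooled contrast the ratio is the mean of 1 (the 1-hour arm) and the value above. At f = 0.5 that gives (1 + 2.50)/2 = 1.75 or (1 + 1.44)/2 = 1.22; at f = 1, 2.5 or 1.44. These figures leave out the case meetings, whose effect cannot be quantified from the documents.

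**What the board might see.** Assume 0.2 events per child over 6 months in usual care (not in the documents), so 18 × 0.2 = 3.6 expected. At f = 0.5 the 4-hour arm expects 3.6 × 2.5 = 9.0 or 3.6 × 1.44 = 5.2. Treating counts as independent Poisson and ignoring clustering, the 4-hour arm shows the higher count with probability 0.92 or 0.64. At f = 0 the probability is 0.42; it is below one half because ties are possible.

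**The case against.** The strongest reply is that the detection route is assumed. The protocol does not say that treating clinicians report events; it names study personnel, and research contact is not stated to rise with dose. Clinicians are observed monthly in all groups, including usual care (Clinician Fidelity), and three sessions are observed per family, with the same payment schedule for ImPACT clinicians (Subject Compensation). The service-use interviews have one schedule for all families. This stands: a reader might infer that the 4-hour arm has four times the observed time, but 4.0 is a ratio of delivered study-session hours. The monthly field visit is likewise a weak asymmetry, because usual-care clinicians are also observed monthly.

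A reader might also infer that most of the listed events are seen only by clinicians or staff. The text does not support that. Self-injury and behavior toward parents can be seen by a parent at any hour, and the list is open-ended. Under the COVID-19 changes both ImPACT and usual care are delivered remotely, so extra session hours add on-screen viewing rather than an extra person in the home.

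Third, events that happen because a child has more intervention hours are a genuine consequence of dose. Adjusting only for hours could hide them. This also stands, and is a reason to show more than one denominator.

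Finally, no numeric stopping boundary is tied to these rates, the board may request further data, and real-time reporting does not depend on the comparison. That limits the consequence. None of these replies supplies a common enquiry or a denominator, or removes the difference in case meetings.

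**Conclusion.** The point holds as a matter of unequal ascertainment. The plan compares rates between groups without a common enquiry or a stated denominator, while the routes by which events reach study personnel differ between arms. Unequal detection can inflate the ImPACT rates. Contact alone could produce an apparent 4-hour v usual-care ratio anywhere from 1.0 (f = 0) to 1.88 or 4.0 (f = 1), depending on which hours count. The 1-hour arm has the same session hours as usual care, so for that arm the concern rests on the case meetings alone.

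It would be too strong to say that the comparison will show more harm at the higher dose. The size depends on f, which the documents do not give, and the bias from contact vanishes at f = 0. Nor can any excess be called pure artefact, since part may be a real effect of dose. The sentence on rates also sets intervention against control without singling out the 4-hour arm, so the smaller pooled figures apply under one reading. The weakness lies in safety data collection and does not touch the efficacy analysis, but it should be corrected because the board relies on this comparison.

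**What to change.** Add one adverse event question set, worded identically in all arms, to the parent service-use interviews already scheduled at 3 and 6 months. Use the answers, per child-month and separately for each of the three arms, as the main between-group comparison. With full follow-up the denominator is 18 × 6 = 108 child-months per arm.

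Alongside it, show all events from every source, per child and per contact hour, by arm. This should not be replaced by the parent interview alone, which would drop events witnessed only by clinicians or staff. Contact hours can come from the session logs already planned for Aim 2 and from the Service Utilization Survey. For 18 children over 26 weeks, planned study-session hours are 18 × 26 = 468 in usual care and in the 1-hour arm, and 18 × 104 = 1,872 in the 4-hour arm. For all services they are about 1,591 (18 × 88.4) and 2,995 (18 × 166.4).

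Real-time reporting stays unchanged. The cost is a few minutes per interview, reliance on parent recall over about 3 months, and one more table. No visit is added.
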